8.2.3 Vital signs

The following vital signs variables will be summarized: systolic blood pressure (mmHg), diastolic blood pressure (mmHg), body temperature (°C) and pulse rate (beats/min).

The change from Baseline table will be presented using descriptive statistics by PS0011 treatment group. The table presentations will display descriptive statistics for the PS0011

Baseline followed by descriptive statistics for the change from PS0011 Baseline results by scheduled visit for PS0011.

The following summaries will be provided:

- A summary of the absolute and change from PS0011 Baseline value for each vital sign variable by PS0011 treatment group and visit
- A summary of the number and percentage of subjects experiencing at least one markedly abnormal value for a vital sign variable as defined in [Table 8-5](#), by PS0011 treatment group and visit.

Table 8–5: Definitions of markedly abnormal blood pressure values

Parameter (unit)	Markedly Abnormal Low	Markedly Abnormal High
Systolic blood pressure (mmHg)	<90 and a decrease from Baseline of ≥ 20	>180 and an increase from Baseline of ≥ 20
Diastolic blood pressure (mmHg)	<50 and a decrease from Baseline of ≥ 15	>105 and an increase from Baseline of ≥ 15

A by-subject listing of all vital signs data will be provided. This listing will be presented by PS0011 treatment group and will include: center, subject identifier, age, gender, race, weight, visit, vital sign variable and result (with abnormal values flagged as “L” or “H” accordingly).

8.2.4 Physical examination

A physical examination is conducted at PS0011 Baseline, Week 48 visit and SFU visit. Findings are collected as AEs and will be listed as such.

8.2.5 Electrocardiograms

A summary of the number and percentage of subjects with normal, abnormal not clinically significant and abnormal clinically significant ECG results at all applicable visits will be presented by PS0011 treatment group.

The change from Baseline tables will be presented using descriptive statistics by PS0011 treatment group. The table presentations will display descriptive statistics for the PS0011 Baseline followed by descriptive statistics for the observed and change from PS0011 Baseline results by scheduled visit for PS0011.

The following ECG variables will be summarized (observed values and change from PS0011 Baseline) by visit: QTcF, RR, PR, QRS, and QT.

QTc abnormalities are defined as QTcF values following dosing that are greater than 450 ms or are increases from PS0011 Baseline greater than 30 ms. QTcF outliers will be highlighted in the data listings and summarized using the following categories:

- Values >450 ms, >480 ms, >500 ms
- Increase from PS0011 Baseline of >30 ms, increase from PS0011 Baseline of >60 ms, increase from PS0011 Baseline of >90 ms
- Values >450 ms and increases from PS0011 Baseline of >30 ms, values >500 ms and increases from PS0011 Baseline of >60 ms.

The number and percentage of subjects who meet the ECG outlier criteria at any assessment post-date of first dose in PS0011 will be summarized by PS0011 treatment group.

A by-subject listing of all 12-Lead ECG data will be provided.

8.2.6 Exposure

The number of doses received will be summarized by PS0011 treatment group over the 48 week administration period. Each dose should consist of two injections.

Extent of exposure to study medication in PS0011 will be summarized using descriptive statistics by PS0011 treatment group.

[figure not shown]
Subject exposure at risk in days in PS0011 will also be summarized using descriptive statistics by PS0011 treatment group. Total subject exposure at risk in years for each PS0011 treatment group will also be provided.

8.2.7 Assessment and management of TB and TB risk factors

A by-subject listing of all the “Evaluation of signs and symptoms of tuberculosis” questionnaire data will be provided.

8.2.8 Electronic Columbia Suicide Severity Rating Scale

The results of the Columbia Suicide Severity Rating Scale (C-SSRS) will be summarized using number of subjects and percentages with (i) events in suicidal behavior, (ii) suicidal ideation, (iii) suicidal behavior and ideation, and (iv) self-injurious behavior without suicidal intent.

Self-injurious behaviour without suicidal intent is defined as an event in the category non-suicidal self-injurious behavior.

The incidence of subjects with suicidal behavior and self-injurious behavior will be summarized by PS0011 treatment group and visit. A by-subject listing of the electronic C-SSRS questionnaire data will be provided.

9 PHARMACOKINETICS

9.1 Pharmacokinetics

Descriptive statistics for the plasma concentrations at PS0011 Baseline will be presented followed by descriptive statistics for the observed and change from PS0011 Baseline results for scheduled visits in PS0011. For the descriptive statistics, geometric mean, geometric coefficient of variation, and 95% confidence interval for the geometric mean will be used instead of the arithmetic mean and standard deviation. The median, minimum, and maximum will also be displayed.

If bimekizumab plasma concentration measurements are deemed to be below the level of quantification (BLQ), then for calculation of the derived statistics this sample result will be set to half the lower level of quantification (LLQ). The subjects with at least one result that is defined as BLQ will also be listed within the respective analysis table. Descriptive statistics will be calculated if at least 2/3 of the values are above the LLQ. If this is not the case, only median, minimum, and maximum will be presented.

If the dosing for a visit is +/- 7 days out of window, then the plasma concentration from that visit and all subsequent visits will be excluded from the PK summary.

The bimekizumab concentrations, including the concentrations excluded from the summaries, will also be listed.

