2.2.1 Clinical

Three clinical studies of bimekizumab have been completed: UP0008 in 39 subjects with mild to moderate plaque psoriasis, RA0124 in 30 healthy volunteers, and PA0007 in 53 subjects with psoriatic arthritis. Two studies (RA0123 and UP0031) are ongoing in subjects with moderate to severe rheumatoid arthritis and in healthy subjects, respectively.

UP0008 was a Phase 1, single ascending dose study in adults with mild to moderate psoriasis affecting $\leq 5\%$ BSA. In this blinded study, single doses of up to 640mg (approximately 8mg/kg in an 80kg adult) were evaluated without any safety concerns. A total of 26 subjects with psoriasis with less than 5% of body surface involvement were treated with a range of single iv doses from 8 to 640mg. There were no clinically relevant safety findings identified at any dose and all doses were well tolerated. The pre-specified exploratory assessment of disease activity showed clinically relevant and statistically significant improvements at the higher doses studied.

RA0124 was a Phase 1, open-label, parallel-group, single-dose study in healthy subjects. The primary objective of this study was to determine the absolute bioavailability of single sc doses of bimekizumab (80mg and 160mg). The secondary objectives were to evaluate the dose proportionality of bimekizumab 80mg and 160mg sc, and to evaluate the safety and tolerability of these sc doses and 160mg given by iv infusion. In RA0124, the absolute bioavailability was similar for the 2 doses tested (0.656 and 0.631 for the bimekizumab 80mg and 160mg sc doses, respectively). The PK of bimekizumab was linear in the tested dose range and the median $t_{1/2}$ following sc administration was similar to that following iv administration (27.81 days and 28.25 days for bimekizumab 160mg sc and 160mg iv, respectively).

Bimekizumab has also been investigated in a Phase 1b, proof of concept, randomized, placebo-controlled, multiple dose study (PA0007). The primary objective of PA0007 was to assess the safety and PK of multiple dose administration of iv bimekizumab in subjects with psoriatic arthritis. Four active doses and a placebo were tested. Drug was administered as a loading dose at Week 0, and 2 additional doses were administered at Week 3 and Week 6. In each treatment group, subjects received a total of 3 doses of bimekizumab, administered every 3 weeks as shown below:

- 80mg loading dose followed by 40mg at Weeks 3 and 6

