14.4 Planned PK analyses

Pharmacokinetic variables will be analyzed for all subjects in the PK-PPS.

Bimekizumab plasma concentrations will be summarized by PS0010/PS0011 treatment group at each scheduled visit. Descriptive statistics for the plasma concentrations at PS0010 Baseline will be presented followed by descriptive statistics for the observed, change from PS0010 Baseline, and change from PS0011 Baseline results for scheduled visits in PS0011. Summarizing in this manner based on the PS0010/PS0011 treatment group will allow for an evaluation of how changing doses (where applicable) impacted plasma concentrations relative to both the original (PS0010) Baseline as well as the new (PS0011) Baseline. For the descriptive statistics, geometric mean, geometric coefficient of variation, and 95% confidence interval for the geometric mean will be used instead of the arithmetic mean and standard deviation.

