3 DATA ANALYSIS CONSIDERATIONS

3.1 General presentation of summaries and analyses

Statistical analysis and generation of tables, figures, subject data listings, and statistical output will be performed using SAS Version 9.3 or higher. All tables and listings will use Courier New font size 9.

Descriptive statistics will be displayed to provide an overview of the study results. For categorical variables, the number and percentage of subjects in each category will be presented. Unless otherwise noted, all percentages will be displayed to one decimal place. No percentage will be displayed for zero counts, and no decimal will be presented when the percentage is 100%. For continuous variables, descriptive statistics will include number of subjects with available measurements (n), arithmetic mean, standard deviation (SD), median, minimum, and maximum. For bimekizumab PK concentrations, summary statistics will include geometric mean, geometric coefficient of variation (CV), 95% confidence interval for the geometric mean, median, minimum, and maximum. All summaries of PK variables will be based on the observed values. No imputation will be used.

Decimal places for descriptive statistics will always apply the following rules:

- “n” will be an integer
- Mean, SD, and median will use one additional decimal place compared to the original data
- CV[%] will be presented with one decimal place
- Minimum and maximum will have the same number of decimal places as the original value.

A complete set of data listings containing all documented data as well as calculated data (eg, change from Baseline) will be generated and will be presented by PS0010/PS0011 treatment group.

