3.5.4 Other analysis sets

3.5.4.1 Pharmacokinetics Per Protocol Set

The PK-PPS is a subset of the FAS, consisting of those subjects who had no important protocol deviations affecting the pharmacokinetic variables, as confirmed during ongoing data cleaning meetings prior to database lock.

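### SAP 9.1 prescribes geometric mean, geometric CV and 95% CI for change from Baseline in plasma concentration, and these do not exist once any change is zero or negative

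*SAP*

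**What the plan says.** SAP 9.1 presents PS0011 Baseline concentrations, followed by "descriptive statistics for the observed and change from PS0011 Baseline results for scheduled visits in PS0011". The next sentence names the geometric mean, the geometric CV and a 95% interval, and says that these "for the geometric mean will be used instead of the arithmetic mean and standard deviation". It adds: "The median, minimum, and maximum will also be displayed". Nothing separates the observed rows from the change rows.

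Protocol 14.4 is built the same way but covers two baselines: "change from PS0010 Baseline, and change from PS0011 Baseline results for scheduled visits in PS0011". It gives the purpose of the layout as an "evaluation of how changing doses (where applicable) impacted plasma concentrations".

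SAP 3.1 has a general rule: "For bimekizumab PK concentrations, summary statistics will include geometric mean, geometric coefficient of variation (CV", and so on. It names concentrations and does not mention change in concentration. Neither document defines PK change as a ratio or as a difference of logarithms.

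SAP 9.1 also has two rules for low concentrations. Values below quantification are set to half the LLQ. If fewer than two thirds of values exceed the LLQ, only median, minimum and maximum are shown.

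**The concern.** A change from Baseline is a signed difference, and geometric statistics are defined only for positive quantities. If any subject in a cell has a change of zero or below, the three headline statistics for that cell cannot be produced as specified.

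The protocol wants these rows in order to see what a dose change does to concentrations, and the cells most likely to fail belong to the one group whose dose goes down. The SAP does not say what the programmer should do then. If non-positive values were silently dropped, the cell would be biased upward and could show a rise where levels fell. Neither document says that this would happen, but neither rules it out.

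**Working it through.** The documents give no figure on this point, so there is none to reproduce. The check has two parts: the definitions, and whether non-positive changes will occur.

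**1. Definitions.** For values x:
- geometric mean = exp(mean(ln x))
- geometric CV = sqrt(exp(SD(ln x)²) − 1)
- 95% CI = exp(mean(ln x) ± t·SD(ln x)/√n)

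All three need x > 0 for every subject. The set (5, 3, −1, 4) has no geometric mean because ln(−1) does not exist. The set (5, 0, 3) has no SD of logs, hence no CV or CI. Setting concentrations to half-LLQ makes them positive, but the difference of two positive numbers can still be zero or negative. The two-thirds rule looks at quantifiability, not at the sign of the change.

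**2. Model inputs.**
- Half-life about 28 days. Protocol 2.2.1 reports "27.81 days and 28.25 days for bimekizumab 160mg sc and 160mg iv, respectively" after single doses in healthy volunteers; using it here is an extrapolation. Range tried: 21 to 35 days.
- Three Q4W doses in PS0010, then 12 in PS0011 (SAP 7: 24 injections, two per dose).
- SFU sample 140 days after the last dose (Protocol Table 5–1).
- Within-subject CV 15 to 40% and between-subject CV 30% are assumptions; the documents give neither.

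**3. Expected troughs**, in dose units, ignoring absorption: c ← (c + dose) × 0.5^(28/half-life). At 28 days the factor is 0.5.
- 480-to-320: 240, 360, then Baseline 420. Week 4: (420 + 320)/2 = 370, change −50. Week 48: 320, change −100. SFU, 112 days (four half-lives) later: 320/16 = 20, change −400.
- 320-to-320: Baseline 280, Week 48 320, change +40.
- Loading dose then 160mg, continuing on 160mg: Baseline 160, Week 48 160, change 0.
- SFU change across all groups on drug at PS0011 Baseline: −46 (64-to-160) to −400.

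The Week 48 change for 480-to-320 is −86 at 21 days and −93 at 35 days, so the sign does not depend on the half-life.

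**4. Share of subjects with Week 48 change ≤ 0:** Φ(−ln(c48/c0) / sqrt(2·ln(1 + CV²))).

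Example for 480-to-320 at CV 15%: ln(320/420) = −0.272; sqrt(2·ln 1.0225) = 0.211; Φ(1.29) = 0.90.

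| Half-life 28 days | CV 15% | 20% | 30% | 40% |
|---|---|---|---|---|
| 480-to-320 | 0.90 | 0.83 | 0.74 | 0.69 |
| Constant dose, no loading | 0.26 | 0.32 | 0.37 | 0.40 |

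Over half-lives of 21 to 35 days and CV 15 to 40%, the ranges are 0.64 to 0.95 and 0.16 to 0.45. Loading-dose subjects continuing on 160mg are at 0.50 at 28 days.

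**5. Chance that a cell fails.** One such subject is enough. For an illustrative group of 10 at a 26% share: 1 − 0.74^10 = 0.95. At the lowest share, 16%: 1 − 0.84^10 = 0.83.

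**6. If only positive changes were kept** (simulation of 2,000,000 480-to-320 subjects at Week 48, half-life 28 days): the geometric mean change would be about +21, +32 and +53 at CV 15, 20 and 30%. The median change in the same subjects is −91.0, −89.6 and −86.5. The geometric mean ratio to Baseline is 320/420 = 0.76, which states the fall correctly.

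**The case against.** The best counter-argument is that SAP 3.1 makes arithmetic mean and SD the default for continuous variables and reserves geometric statistics for concentrations, so change would fall under the default. That reading is coherent. But 9.1 is the more specific section, names change explicitly, and says that arithmetic mean and SD are replaced. At best the two sections are ambiguous.

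Several lesser points stand in part:
- The two-thirds rule may already suppress some SFU cells in low-dose groups; the modelled 64-to-64 level there is about 4 against a steady trough of 64. The LLQ is not stated, so this cannot be settled. On-treatment troughs in the 480-to-320 group are not expected to trigger the rule.
- By the bare product definition, a geometric mean that includes a zero equals zero. The CV and CI still fail.
- The reported 160-to-160 group pools subjects with and without the loading dose, so the constant-dose row does not describe that cell exactly. Pooling raises the share at or below zero, because loading-dose subjects sit near one half.
- The upward bias depends on a programming choice that nobody has planned.
- Arithmetic mean and SD are also legitimate for signed changes.

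None of these makes the rule as written computable.

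**Conclusion.** The concern holds. It rests on the wording and on the definition of a logarithm; the PK model only shows how often the problem would arise. Negative changes are expected in the 480-to-320 group at each modelled on-treatment visit, and at SFU in every group that was on drug at PS0011 Baseline. On a constant dose, ordinary variation is enough to make it near certain that a cell of moderate size contains at least one. The percentages depend on the assumed within-subject CV and the extrapolated half-life.

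The consequence is modest. PK is an 'other' objective and all summaries are descriptive. The observed geometric means, the median, minimum and maximum of change, and the listings would still show the fall. It should be corrected, but it does not threaten any safety or efficacy conclusion.

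**What to change.** In SAP 9.1, restrict geometric mean, geometric CV and 95% CI to:
1. observed concentrations; and
2. the ratio of each visit to PS0011 Baseline, calculated from log ratios with the existing half-LLQ substitution, stating that the two-thirds rule must be met at both time points.

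Summarise absolute change by median, minimum and maximum, which are already planned. Arithmetic mean and SD may be added if wanted.

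Do not present ratios where the Baseline is drug-free: placebo-to-placebo and placebo-to-160mg at PS0011 Baseline, and any PS0010 Baseline under Protocol 14.4. Show observed values there. SAP 3.5.4.1 defines the population this way: "The PK-PPS is a subset of the FAS, consisting of those subjects who had no important protocol deviations affecting the pharmacokinetic variables". It does not require a quantifiable concentration, so placebo subjects can be included, and their ratio would be half-LLQ over half-LLQ = 1, an artefact.

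A smaller alternative is to omit the ratio and limit the change rows to median, minimum and maximum.

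The cost is a wording change in 9.1, one derivation with its table rows, and a matching edit or SAP note for Protocol 14.4. The only thing given up is a set of geometric cells for absolute change that could not be reliably produced.

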9.2 Immunogenicity

9.2.1 Anti-bimekizumab antibodies

Subjects with a positive on-treatment (i.e., excluding PS0010 Baseline) anti-BKZ antibody result in either PS0010 or PS0011 will be classified as anti-BKZ positive.

Anti-BKZ antibody status will be summarized for each PS0010/PS0011 treatment group at each scheduled PS0010 and PS0011 visit using the PK-PPS analysis set. The first occurrence of anti-BKZ antibody positivity will also be presented for each PS0010/PS0011 treatment group at each scheduled PS0010 and PS0011 visit.

The anti-BKZ antibody status will be determined for each visit where samples are taken for drug concentration means. The cut point for determining whether the anti-bimekizumab antibody level is sufficiently high to be considered anti-BKZ antibody positive is not yet known. However, this will be determined prior to the database lock of the PK and anti-BKZ antibody data.

A line plot of the percentage of anti-BKZ antibody positive subjects at each visit will be produced by PS0010/PS0011 treatment group. All individual subject-level anti-BKZ antibody results will be listed.

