- Bimekizumab 320mg administered sc Q4W
- Bimekizumab 480mg administered sc Q4W
- Placebo administered sc Q4W

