^a Visit windows of ±3 days from the first dose (Baseline) at all visits except SFU, which has a window of -3 and +7 days from scheduled visit date.

^b The SFU Visit will occur 20 weeks after the last dose of bimekizumab or placebo.

^c Ensure that the informed consent for PS0011 was completed by the subject during the Week 8 or Week 12 Visit of PS0010 (must be done before any study assessments are performed for PS0011).

^d To be performed prior to the first dose of bimekizumab or placebo in PS0011.

^e Includes evaluation of signs and symptoms of active TB and risk for exposure to TB.

^f The noted PS0011 Baseline assessments will be obtained at the Week 12 Visit of PS0010 and do not need to be recorded on the case report form for this study.

^g Vital signs (blood pressure, pulse rate, and temperature) are to be measured prior to blood sampling and prior to dosing, where applicable.

^h Pregnancy testing will be urine testing at all visits except SFU, which will be a serum test.

ⁱ It is recommended that the QuantiFERON TB GOLD test be performed.

^j Ensure that an IGRA test was performed during the Week 8 Visit of PS0010 and the result was negative.

^k All blood samples are to be taken prior to dosing.

^l Including assessment for the development of different forms of psoriasis at the SFU visit.

^m Subjects who received placebo or bimekizumab 64mg, 160mg, or 320mg loading dose + 160mg Q4W in PS0010 must achieve PASI90 response at Week 12 in PS0010 to enter the PS0011 extension study on the same treatment dose. Subjects who do not achieve PASI90 response at Week 12 in PS0010 while receiving placebo or bimekizumab 64mg will be assigned to receive bimekizumab 160mg on entering PS0011. Subjects who do not achieve PASI90 response at Week 12 in PS0010 while receiving bimekizumab 160mg or 320mg loading dose + 160mg will be assigned to receive bimekizumab 320mg Q4W on entering PS0011. Subjects who receive bimekizumab 320mg or 480mg Q4W in PS0010 will be assigned to receive bimekizumab 320mg Q4W on entering PS0011, regardless of their PASI90 response at Week 12 in PS0010. Any subject who does not achieve PASI75 response at Week 12 or later in PS0011 will be withdrawn from study treatment and will return to complete the Early Withdrawal Visit assessments.

[figure not shown]

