14.2 General statistical considerations

No inferential statistical analyses are planned for this extension study. Instead, all variables will be presented using summary statistics. For categorical variables, counts and percentages will be displayed. For continuous variables, summary statistics will consist of the number of available observations, arithmetic mean, standard deviation, median, minimum, and maximum unless stated otherwise.

Because subjects entering PS0011 may or may not be continuing on the same dose as that received in PS0010, there are various combinations of treatment that could be received when considering both PS0010 and PS0011 together. For describing the summaries to be produced, treatment groups will be categorized as either the PS0011 treatment groups or PS0010/PS0011 treatment groups. These categorizations are outlined below.

PS0011 treatment groups

This refers to the study treatment assigned to the subject at the beginning of PS0011 and does not account for the treatment received in PS0010. The PS0011 treatment groups are as follows:

- Placebo
- Bimekizumab 64mg Q4W
- Bimekizumab 160mg Q4W
- Bimekizumab 320mg Q4W
- All Bimekizumab (optional – to be used only if specified)

PS0010/PS0011 treatment groups

This refers to the combination of the randomized treatment in PS0010 and the treatment assigned at the beginning of PS0011. Some groups have been combined where it is considered appropriate to do so. The PS0010/PS0011 treatment groups with descriptions are as follows:

- Placebo to Placebo – Subjects randomized to placebo in PS0010 who achieve PASI90 response at Week 12 of PS0010 and continue to receive placebo in PS0011.
- Placebo to Bimekizumab 160mg Q4W – Subjects randomized to placebo in PS0010 who do not achieve PASI90 response at Week 12 of PS0010 and are treated with bimekizumab 160mg Q4W in PS0011.
- Bimekizumab 64mg to Bimekizumab 64mg – Subjects randomized to bimekizumab 64mg Q4W in PS0010 who achieve PASI90 response at Week 12 of PS0010 and continue to receive bimekizumab 64mg Q4W in PS0011.
- Bimekizumab 64mg to Bimekizumab 160mg – Subjects randomized to bimekizumab 64mg Q4W in PS0010 who do not achieve PASI90 response at Week 12 of PS0010 and are treated with bimekizumab 160mg Q4W in PS0011.

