4.7 Examination of subgroups

Subgroup analyses will be performed on the secondary efficacy variables.

The following subgroup analyses will be performed:

- Age (<65 years, ≥65 years)
- Gender (male, female)
- Duration of disease at PS0010 Baseline (<median, ≥median)
- Region (North America [Canada, USA], Europe and Asia [Czech Republic, Hungary, Poland, Japan])
- Body weight at PS0010 Baseline (<100 kg, ≥100 kg)
- Body Mass Index (BMI) at PS0010 Baseline (<25 kg/m², 25 to <30 kg/m², ≥30 kg/m²)
- Prior biologic systemic therapy at PS0010 Baseline (yes, no)

- Prior anti-TNF therapy at PS0010 Baseline (yes, no)
- Any prior systemic therapy at PS0010 Baseline (yes, no)
- Anti-bimekizumab antibody positivity at any time on treatment during PS0010 or PS0011 (yes, no)
- PASI score at PS0010 baseline (<20, ≥20)
- Psoriasis BSA at PS0010 baseline (<20%, ≥20%).

These summaries, using the FAS, will be based on imputed data (NRI) and will include descriptive statistics only. If there are less than 2 subjects in any subgroup category/treatment group, then that subgroup category will not be summarized. If it is possible to collapse subgroups with more than 2 categories, then collapsing may be done to get categories with no less than 2 subjects per subgroup category/treatment group.

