8.2 Other safety analysis

8.2.1 TEAEs

The following summaries will be provided by PS0011 treatment group and for the “All bimekizumab” group. In addition, all summaries of TEAEs “per 100 subject years” will display EAIR and EAER:

- Incidence of TEAEs – Overview
- Incidence of TEAEs per 100 subject years by SOC, HLT and PT
- Incidence of TEAEs per 100 subject years by SOC, HLT, PT and by Timing of Onset Relative to Anti-bimekizumab Antibody Status
- Incidence of TEAEs by Decreasing Frequency of PT
- Incidence of TEAEs by Maximum Severity, SOC, HLT and PT
- Incidence of Non-Serious TEAEs by SOC, HLT and PT
- Incidence of Non-Serious TEAEs Above Reporting Threshold of 5% by SOC and PT

The incidence of TEAEs per 100 subject years will also be summarized for PS0010 and PS0011 combined, where treatment emergence and exposure at risk are relative to the first dose of study drug in PS0010. In the case of a subject that switches study treatment when starting PS0011, exposure at risk to PS0010 treatment will end the day prior to the first PS0011 dose. Adverse events that occur on the PS0011 baseline visit date will be attributed to the PS0010 treatment.

The only exception to this definition is for the following types of events:

- Those that code to a High Level Term (HLT) of “Injection Site Reactions”
- Those which have been designated as an Injection Reaction on the AE CRF and do not code to a System Organ Class (SOC) of “Investigations”
- Those which have been identified as a hypersensitivity reaction or an anaphylactic reaction

When any of these events occur on the date of treatment switch at PS0011 Baseline, the AE will be attributed to the treatment initiated in PS0011.

All AE summaries will be ordered alphabetically by SOC and HLT within SOC and in terms of decreasing frequency for PT within HLT in the “All bimekizumab” treatment group.

For each subject and each AE, the worst severity recorded will be attributed and used in the by-severity summaries. Similarly, the worst causality (most related to treatment) will be attributed and used in the by-causality summaries. If severity or causality is missing, the worst case will be assumed.

If the intensity of an AE is unknown, it will be considered as severe. If the relationship to study drug is missing, it will be considered as related.

Additional tables will summarize TEAEs by relationship to study medication, TEAEs leading to withdrawal from the study, treatment-emergent SAEs, and deaths:

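### The anti-bimekizumab antibody flag in SAP 9.2.1 counts PS0010 placebo-period samples as on-treatment, so placebo-origin subjects can be classed positive without any bimekizumab exposure

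*SAP*

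**What the plan says.** **The rule.** SAP 9.2.1 states: "Subjects with a positive on-treatment (i.e., excluding PS0010 Baseline) anti-BKZ antibody result in either PS0010 or PS0011 will be classified as anti-BKZ positive". It sets no condition on the treatment received. It also tabulates antibody status and first positivity for every PS0010/PS0011 treatment group at each scheduled visit of both studies, on the PK-PPS.

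**The placebo-origin subjects.** One PS0010 regimen is "Placebo administered sc Q4W" (Protocol 2.2.1). Protocol 14.2 divides its continuing subjects into two groups:
- Placebo to Bimekizumab 160mg, first exposed in the extension: "Subjects randomized to placebo in PS0010 who do not achieve PASI90 response at Week 12 of PS0010 and are treated with bimekizumab 160mg Q4W".
- Placebo to Placebo: those who "achieve PASI90 response at Week 12 of PS0010 and continue to receive placebo in PS0011".

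**The samples.** Protocol Table 5-1 marks the PS0011 Baseline antibody sample with footnote f: "The noted PS0011 Baseline assessments will be obtained at the Week 12 Visit of PS0010". Footnote k adds: "All blood samples are to be taken prior to dosing".

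**Where the status is used.** SAP 4.7 lists, as a subgroup for the secondary efficacy variables, "Anti-bimekizumab antibody positivity at any time on treatment during PS0010 or PS0011 (yes, no". SAP 8.2.1 plans a TEAE table "by Timing of Onset Relative to Anti-bimekizumab Antibody Status", presented by PS0011 treatment group and for all bimekizumab groups together.

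**The concern.** The evident reason for leaving out PS0010 Baseline is that the sample precedes drug. In the PS0010 placebo arm every later PS0010 sample also precedes drug, yet the rule keeps those samples. A positive result there reflects assay background or pre-existing reactivity, not a response to bimekizumab.

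Three outputs are exposed:
- **First positivity (SAP 9.2.1).** A positive during placebo uses up the subject's first occurrence and hides a later first positive after bimekizumab has started.
- **Antibody subgroup (SAP 4.7).** The ever-positive category can include subjects whose only positive sample came before any bimekizumab. SAP 4.7 does not summarise a category with fewer than 2 subjects in a treatment group, so a single false flag can decide whether a small category appears.
- **TEAE table by antibody status (SAP 8.2.1).** This may be affected, depending on how its timing categories are defined. It pools Placebo to 160mg subjects with the other 160mg subjects, so a false flag would not be visible there.

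**Working it through.** The documents state no figure on this point, so there is none to reproduce. The check has two parts.

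**1. Applying the rule**

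| Subject | Positive sample | Bimekizumab doses before it | Status under SAP 9.2.1 |
|---|---|---|---|
| Placebo to 160mg | PS0010 Week 12 only | 0 | Positive |
| Placebo to Placebo | Any visit after PS0010 Baseline | 0 | Positive |

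Three provisions might have prevented this. None does.
- **Meaning of on-treatment.** The bracketed explanation in SAP 9.2.1 supplies the definition, and Protocol 7.1 counts placebo as investigational product. The term therefore does not mean on bimekizumab.
- **Analysis set.** The PK-PPS in SAP 3.5.4.1 is the FAS without deviations affecting PK. It does not carry the requirement in Protocol 14.1 for a quantifiable postdose concentration, so never-exposed subjects stay in. Even the protocol's set would keep Placebo to 160mg subjects.
- **Switch rule.** For the combined PS0010 and PS0011 adverse-event tables, SAP 8.2.1 ends PS0010 exposure the day before the first PS0011 dose when treatment changes. Antibody status has no counterpart.

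**2. Illustrative scale**

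Inputs:
- Placebo-origin subjects at risk: 240 planned for PS0010 (Protocol 14.8). Protocol 2.2.1 lists six regimens but prints a five-term ratio, so 240/6 = 40 or 240/5 = 48. All are assumed to continue.
- Placebo-period samples, k: 1 to 3 (assumption). The documents establish only the Week 12 sample.
- Later PS0011 samples: 8, at Weeks 4, 8, 12, 16, 28, 40 and 48 and the SFU Visit (Protocol Table 5-1).
- False-positive rate per sample, f: 1% to 5%, independent between samples (assumption). SAP 9.2.1 says the cut point is not yet known.

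The chance of at least one false positive among the k placebo-period samples is 1 − (1 − f)^k:
- f = 1%, k = 1: 1.0%, or 0.4 of 40.
- f = 5%, k = 3: 1 − 0.95^3 = 14.3%, or 5.7 of 40.

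Some of those subjects would also be positive on a later sample and so be flagged under any rule. The share flagged solely because of placebo-period samples is (1 − f)^8 × [1 − (1 − f)^k]:
- f = 1%, k = 1: 0.99^8 − 0.99^9 = 0.9227 − 0.9135 = 0.9%, or 0.4 of 40 (0.4 of 48).
- f = 5%, k = 1: 0.95^8 − 0.95^9 = 0.6634 − 0.6302 = 3.3%, or 1.3 of 40.
- f = 5%, k = 3: 0.95^8 − 0.95^11 = 0.6634 − 0.5688 = 9.5%, or 3.8 of 40 (4.5 of 48).

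The second calculation measures what a corrected rule would change for a subject who goes on to receive bimekizumab. For a Placebo to Placebo subject all nine known samples (PS0011 Baseline plus eight) are drug-naive. The chance of a false flag is then 1 − 0.99^9 = 8.6% to 1 − 0.95^9 = 37.0%.

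**The case against.** The best case on the other side is that little depends on this flag. No inferential analysis is planned (Protocol 14.2), immunogenicity ranks among the other objectives, and the antibody subgroup is one of twelve descriptive subgroups. The by-visit tables, the first-positivity table and the line plot are split by PS0010/PS0011 group, and every individual result is listed, so placebo-period positives can be found. All of this stands. It confines the problem to the subject-level flag and its uses, but it does not make the flag right.

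The remedy is also partial. A subject with persistent pre-existing reactivity stays positive on post-dose samples, and so does an active-arm subject already reactive at PS0010 Baseline. Under the illustrative model, eight later samples alone give 1 − 0.99^8 = 7.7% to 1 − 0.95^8 = 33.7% false flags. The correction closes one route to false positivity, not all of them.

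Three stronger readings are tempting and the documents do not support them:
- *Placebo to 160mg is the only group that starts 160mg drug-naive.* That is true only within PS0011. The PS0010 160mg arm without a loading dose also began there, and SAP 9.2.1 displays its PS0010 visits.
- *Every PS0011 TEAE of a falsely flagged subject would count as following antibody development.* This rests on a table title. The SAP neither defines the timing categories nor says that they use the 9.2.1 flag. It would follow only if the table were anchored on first positivity.
- *About 40 subjects are affected, with up to 5.7 misclassified.* Forty is the number at risk. The 5.7 includes subjects who would be positive later anyway. It also treats samples as independent, whereas pre-existing reactivity would recur within a subject.

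**Conclusion.** As written, the SAP can class a subject as anti-bimekizumab positive with no bimekizumab exposure, and neither document has a rule that prevents it. This follows from the text and does not depend on any assumed assay rate. At least one qualifying sample, PS0010 Week 12, is certainly drug-naive in every placebo-origin subject.

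The practical effect is modest. By-visit prevalence is unaffected. The flag, the first-positivity table and the SAP 4.7 subgroup are affected, and the SAP 8.2.1 table is affected only if it is anchored on first positivity. The figure of about 0.4 to 3.8 of 40 subjects rests on six equal arms, full continuation, complete later sampling, independence, one to three placebo-period samples and a 1% to 5% false-positive rate. Only the later sampling schedule comes from the documents. The range shows scale and is not an estimate. The definition should be corrected because a small antibody-positive category can be altered by one or two subjects.

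**What to change.** In SAP 9.2.1:
- For subjects randomised to placebo in PS0010, take the last sample before the first bimekizumab dose as the antibody baseline, and count only later samples as on-treatment.
- Leave subjects who never receive bimekizumab out of the positive class.
- Keep the by-visit display of placebo-period results, reported separately as assay background.

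Apply the same definition to the subgroup in SAP 4.7 and to the TEAE table in SAP 8.2.1, and state how the timing categories of that table are anchored.

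The cost is a sentence or two of SAP text and one derivation condition. No new samples or data are needed. The difference between the protocol and SAP definitions of the PK-PPS should be reconciled separately, since neither version resolves this point for Placebo to 160mg subjects.
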